11.3 Measurement of Response

11.3.1 Baseline Documentation of Target lesions

All treated tumors (GTV1-5) should be identified as the target lesions and recorded and measured at baseline and with each follow-up imaging evaluation. The longest diameter (LD) for the target lesion will be calculated from the treatment planning CT scan using pulmonary windowing and reported as the baseline LD. For follow-up assessment, diagnostic CT scans pulmonary windows are preferred as the method of evaluation for response. Cases in which it is indeterminate whether consolidation represents residual tumor or treatment effect, it should be assumed that abnormalities are residual tumor

11.3.2 Evaluation of Target and Involved Lobe Lesions

Complete Response(CR)	Disappearance of the target lesion; ideally, this determination will be made based on CT image evaluation.
Partial Response(PR)	At least a 30% decrease in the LD of the target lesion, taking as reference the baseline LD; ideally, this determination will be made based on CT image evaluation.
Stable Disease (SD)	Neither sufficient shrinkage to qualify for CR/PR above nor sufficient increase to qualify for LE below, taking as reference the smallest LD since the treatment started
Local Enlargement(LE)	At least a 20% increase in the LD of target lesion, taking as reference the smallest LD recorded since the treatment started; Ideally, this determination will be made based on CT image evaluation.
Primary Tumor Failure (PTF)	Refers to the primary treated tumor after protocol therapy and corresponds to meeting both of the following two criteria: 1) Increase in tumor dimension of 20% as defined above for local enlargement (LE); 2) The measurable tumor with criteria meeting LE should be avid on Positron Emission Tomography (PET) imaging with uptake of a similar intensity as the pretreatment staging PET, OR the measurable tumor should be biopsied confirming viable carcinoma. For outcome analysis, Marginal Failures (MF; see below) will also be counted as PTF; however, they should be distinguished specifically as MF, not PTF, on all report forms. The EORTC criteria for post-treatment PET evaluation will be used as a basis for evaluation in cases more difficult to assign as to whether the uptake is pathological for cancer recurrence vs. inflammation. ⁴⁶
Marginal Failure (MF)	Refers to the appearance after protocol therapy of a measurable tumor appearing since treatment within 1.0 cm of the treated PTV (see Section 6.4) and meeting the following two criteria: 1) Enlarging tumor dimensions corresponding to a 20% increase in the longest diameter compared to initial appearance on imaging evaluation. Ideally, this determination will be made based on CT image evaluation; 2) The measurable tumor within 1.0 cm of the treated PTV should be avid on Positron Emission Tomography (PET) imaging with uptake of a similar intensity as the pre-treatment staging PET, OR the measurable tumor should be biopsied confirming viable carcinoma.
Primary Tumor Control	The absence of Primary Tumor Failure.

(PTC)	
Involved Lobe Failure	Refers to the appearance of lung cancer after protocol therapy within the anatomical boundaries of the lobe in which the primary tumor arose (involved lobe). The measurable tumor apart from the primary tumor but within the involved lobe should meet criteria for LE, should be avid on Positron Emission Tomography (PET) imaging with uptake highly suspicious for cancer (e.g., SUV>3-5), OR the measurable tumor should be biopsied confirming viable carcinoma. Failure outside of the involved lobe (uninvolved lobes) will be considered metastatic disseminated (distant) failures. Local Failure Refers to either primary tumor failure or involved lobe failure or both.
Local Control (LC)	The absence of Local Failure

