3.0 PATIENT SELECTION

3.1 Conditions for Patient Eligibility

- 3.1.1 \geq 18 years of age
- 3.1.2 Pathologic confirmation of primary soft tissue sarcoma with pathologic or radiographic evidence of pulmonary metastatic disease
- 3.1.3 No evidence of extra pulmonary progression of disease for 3 months prior to enrollment on study.
- 3.1.4 1-5 pulmonary lesions all \leq 5 cm in size.
- 3.1.5 Medically inoperable or declines surgery
- 3.1.6 Patients may have had previous treatment for pulmonary metastases

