11.2 PATIENT ASSESSMENTS

11.2.1 Patients will be seen 4 to 6 weeks after the last fraction of radiation therapy, every 6 months for 2 years.

11.2.2 Prior to each visit, a CT of the chest with contrast will be obtained for disease assessment. If there is deemed to be progressive disease, a PET scan will be obtained per discretion of the physician. Biopsy is recommended although will be at the discretion of treating physician. Treatment after failure will be at the treating teams discretion and documented.

11.2.3 QOL assessments will be made using the FACT-L questionnaire. Questionnaires will be given every 6 months for 2 years.

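### A treated lesion that is resected, ablated or re-irradiated before a confirmed failure is still scored as controlled by SBRT, because no rule in 11.3.2 or 12.4 covers later therapy

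*Combined protocol and SAP*

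**What the plan says.** Control is a default state in Section 11.3.2 of the combined protocol and SAP. Primary tumor control is "The absence of Primary Tumor Failure" and local control is "The absence of Local Failure". Primary tumor failure "Refers to the primary treated tumor after protocol therapy and corresponds to meeting both of the following two criteria": a 20% increase in dimension, and either PET avidity or a positive biopsy. Marginal failures count as primary tumor failures in the outcome analysis, and local failure also includes involved lobe failure.

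The response categories rest on size alone. Complete response is "Disappearance of the target lesion; ideally, this determination will be made based on CT image evaluation". Partial response is "At least a 30% decrease in the LD of the target lesion, taking as reference the baseline LD". Neither is conditional on the absence of other treatment.

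Section 11.3.1 has every treated lesion measured at each follow-up scan, and 11.2 schedules CT before each visit. On confirmation, 11.2.2 says "If there is deemed to be progressive disease, a PET scan will be obtained per discretion of the physician", and biopsy is likewise recommended but discretionary. On later therapy it says "Treatment after failure will be at the treating teams discretion and documented". Sections 7 (Drug Therapy) and 8 (Surgery) are marked as not applicable, so they add no rule.

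Section 12.3 judges recurrence lesion by lesion. Section 12.4 reports crude recurrence rates and time to recurrence. The only censoring rule, in 12.3, is for disease-free survival, at last follow-up.

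**The concern.** Once a lesion has been cut out, ablated or irradiated again, later scans show the combined effect of SBRT and the next treatment. If no failure was confirmed first, the written rules keep calling it controlled, and SBRT is credited with what the second treatment did.

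The situation is foreseeable. Section 3.1.5 admits patients who are "Medically inoperable or declines surgery", so some patients may be operable. Patients may have up to five lesions, so progression in one place can prompt treatment that also reaches a stable treated lesion.

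Local control is the first secondary objective in 2.1.2, and the hypothesis in 2.1 is that SBRT controls lesions about as well as resection. Counting a later resection as SBRT control pushes the estimate towards that hypothesis. Obtaining PET or biopsy in every enlarging lesion would not remove the problem, because it also affects lesions that were stable when treated again.

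**Working it through.** **Planning figures.** The schema gives 20 patients and a conservative estimate of 40 tumors. The patient number follows from accrual: (5 + 5 per year) × 2 years = 20. The plan states no target, margin or precision for local control, so there is no local-control figure to reproduce.

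**Step 1: apply the written rules.** Failure = (20% enlargement) AND (PET or biopsy positive). Control = no failure.

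| Course of the treated lesion | Enlarged 20% | Confirmed | Scored as |
|---|---|---|---|
| Stable, then resected, ablated or re-irradiated | No | No | Controlled; literally complete response if gone on CT |
| Enlarged, then treated again without PET or biopsy | Yes | No | Controlled |
| Shrinks under new systemic therapy | No | No | Controlled; partial or complete response |
| Enlarged and confirmed, then salvaged | Yes | Yes | Failure |

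The first two rows are the gap. The third matters less: a lesion without failure is controlled whether or not a drug shrinks it, although a drug could delay a later failure. The fourth row is already handled correctly.

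**Step 2: size on 40 lesions.** The documents do not give the number of failures (f) or of lesions treated again locally without a confirmed failure (k). Both are assumptions.

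- As written: (40 − f)/40
- Those lesions counted as failures: (40 − f − k)/40
- Those lesions removed, a rough stand-in for censoring: (40 − f − k)/(40 − k)

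Each such lesion shifts crude control by 1/40 = 2.5 points if counted as a failure.

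With f = 4 and k = 4:

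- As written: 36/40 = 90% (exact 95% CI 76.3 to 97.2)
- Counted as failures: 32/40 = 80% (64.4 to 90.9)
- Removed: 32/36 = 88.9%

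With f = 4 and k = 2, the last two become 34/40 = 85% and 34/38 = 89.5%.

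**Step 3: vary the failure count.** The values of f were chosen to lie near the 2-year control rates quoted in Section 1.0 (97%, 88% and 77.9%), with k = 4.

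| f | As written | Counted as failures | Removed |
|---|---|---|---|
| 1 | 97.5% | 87.5% | 97.2% |
| 5 | 87.5% | 77.5% | 86.1% |
| 9 | 77.5% | 67.5% | 75.0% |

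The gap is 10 points if all four lesions count as failures, and 0.3 to 2.5 points if they are removed. The intervals treat lesions as independent, although 40 lesions in 20 patients average two per patient, so they are probably too narrow.

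**The case against.** The strongest reply is that the gap is narrow and probably small. Several parts of it stand.

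- A reader might infer that any treated lesion salvaged later counts as controlled. It does not. A failure confirmed before salvage is a local failure and stays in the crude rate and in time to recurrence.
- A reader might infer that a lesion ablated or re-irradiated early can never fail. The definitions have no cut-off at new therapy, so later regrowth can still qualify as primary tumor, marginal or involved lobe failure.
- A reader might infer that the plan declares a resected lesion a complete response. It is silent on this; the result only follows from applying the definition literally. Section 11.3.1 also has indeterminate consolidation assumed to be residual tumor, which works against easy response credit. Response rates are not a listed endpoint in 2.1, 12 or 13.
- A reader might take 10 points as the bias. That figure assumes that all four lesions were treated for true but unconfirmed growth. For lesions that were stable, removal is the relevant comparison, and the shift is about 1 point (90% to 88.9%), well inside the interval.
- Scoring every therapy for suspected growth as a failure would override the two-criterion definition. Section 6.8.3 itself warns that radiology reports may describe progression when the tumor is stable or shrinking, so such a rule could create false failures.

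This is also a 20-patient pilot whose primary objective in 2.1.1 is acute toxicity. What the reply does not remove is that, for a lesion treated again locally with no confirmed failure, the written rules return control, and nothing in 12.4 takes the lesion out of the crude rate.

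**Conclusion.** The point holds for treated lesions that receive further local therapy before a confirmed failure. As the rules are written, they remain successes, and the error favors the hypothesis of control comparable to resection. This is the result of stated definitions, not only of missing detail.

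Its size cannot be derived from the documents. On 40 tumors with 4 assumed failures and 4 assumed lesions of this kind, the effect runs from about 1 point (removed) to 10 points (all counted as failures); the reason for the later therapy decides where in that range the truth lies. The documents do not show how often such therapy will occur. The primary toxicity objective is unaffected. The change is worth making because local control is the leading efficacy measure and the rule is cheap to add.

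**What to change.** Amend 11.3.2 and 12.4 at lesion level. This changes scoring only, not patient care.

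1. Record the date, type, lesion number and reason for any later local therapy to a treated lesion, whether given before or after failure, and the start date of any new systemic therapy.
2. In the main local control analysis, score each lesion only on assessments up to that local therapy. It is a failure if the primary tumor failure criteria are met by then; state that tissue from the resected specimen can supply confirmation when the lesion had already enlarged by 20%. Otherwise censor it at the last CT before the therapy, and do not carry it in the crude rate as a success to the end of follow-up.
3. Add two sensitivity analyses: local therapy given for enlargement without PET or biopsy confirmation counts as failure; and follow-up is censored at the start of new systemic therapy.
4. If complete or partial response is reported, assign it only from scans before any such local or systemic therapy.

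**Cost.** A few sentences and some fields on the follow-up form; therapy after failure is already to be documented, but therapy before failure must be captured too. Local control may come out slightly lower and less precise. Censoring at later local therapy may be informative, since lesions chosen for more treatment may differ from the rest; the first sensitivity analysis shows how far the result depends on this for lesions treated because they had enlarged.

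### A treated lesion that enlarges but never has PET or biopsy is scored as locally controlled, exactly like one that was tested and found negative (11.3.2)

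*Combined protocol and SAP*

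**What the plan says.** In 11.3.2, Primary Tumor Failure (PTF) "corresponds to meeting both of the following two criteria". The first is local enlargement (LE), a rise of at least 20% in longest diameter from the smallest value since treatment started. The second is met either by a biopsy showing viable tumor or by a PET on which the lesion "should be avid on Positron Emission Tomography (PET) imaging with uptake of a similar intensity as the pretreatment staging PET". Primary Tumor Control is "The absence of Primary Tumor Failure", and Local Control is "The absence of Local Failure". Marginal Failure, which counts as PTF for analysis, has the same two-part form.

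Four other places bear on this:

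- **11.1 and 11.2.2:** follow-up PET is at the physician's discretion. Biopsy is recommended but also discretionary. The baseline PET may be left out if insurance does not cover it.
- **11.3.1:** "All treated tumors (GTV1-5) should be identified as the target lesions" and measured at each follow-up imaging. Where consolidation could be either tumor or treatment effect, "it should be assumed that abnormalities are residual tumor".
- **11.3.2, EORTC rule:** the EORTC PET criteria are used "in cases more difficult to assign as to whether the uptake is pathological for cancer recurrence vs. inflammation".
- **12.3 and 12.4:** recurrence is defined lesion by lesion using 11.3.2, and crude rates and time to recurrence are reported. Neither section has a rule for enlargement without confirmation.

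**The concern.** Asking for confirmation is reasonable in itself. The text on bronchial injury (6.8.3) explains that collapsed lung can be reported as progression while the tumor is stable or shrinking. The difficulty is that the definition has two outcomes where three are needed. A lesion that enlarged and tested negative and a lesion that enlarged and was never tested both fall into control, although the second carries no evidence of control.

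Because the physician decides who is tested, the untested lesions need not be a random subset. Where the baseline PET is missing, the PET route also has no comparator, and the plan does not say how it then works.

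Local control is the first-listed secondary objective (2.1.2), and the Introduction says the study is meant to document it. Time to recurrence in 12.4 rests on the same definition.

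**Working it through.** **1. The classification.** The plan gives no target or power figure for local control, so there is no stated number to reproduce. The definitions reduce to PTF = LE and (PET avid or biopsy positive), with control = not PTF.

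| Treated lesion | Criterion 1 | Criterion 2 | Label |
|---|---|---|---|
| LE, PET avid or biopsy positive | met | met | failure |
| LE, tested negative | met | not met | control |
| LE, never tested | met | not met | control |
| No LE | not met | – | control |

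Rows 2 and 3 are scored alike. Involved Lobe Failure cannot catch row 3, because it concerns tumor other than the treated lesion.

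**2. Do other rules close the gap?** The 11.3.1 default points towards tumor, but it does not say that criterion 2 is met or waived. The EORTC rule is about interpreting uptake, so it presupposes that a PET was done. Involved Lobe Failure has its own ambiguity: the tumor "should meet criteria for LE, should be avid on Positron Emission Tomography (PET) imaging with uptake highly suspicious for cancer", with biopsy as an alternative. The sentence does not show whether PET or biopsy is required on top of LE.

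**3. Size, treated lesions only.** The Schema plans for 40 tumors, so one lesion is 1/40 = 2.5 points. Let f = 1 − true control and u = the share of true failures never verified over all follow-up. Assume that every true failure reaches LE and that the tests done are correct. Then reported control = 1 − f(1 − u), and bias = f·u. The true rates are borrowed from the Introduction's cited studies for illustration. The range u = 25% to 75% is an assumption.

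| Assumed true control | u = 25% | u = 75% |
|---|---|---|
| 77.9% | 83.4% | 94.5% |
| 88% | 91.0% | 97.0% |
| 96% | 97.0% | 99.0% |

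At 88%, the bias is 0.12 × 0.25 = 3.0 points (40 × 0.03 = 1.2 lesions) to 0.12 × 0.75 = 9.0 points (3.6 lesions).

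**4. Repeated opportunities.** Six-monthly visits for 2 years (11.2.1) give 24/6 = 4 such visits. If each of k scans showing LE carries an independent chance t of testing, u = (1 − t)^k. At a true 88%:

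| k | 1 | 2 | 3 | 4 |
|---|---|---|---|---|
| Bias, t = 0.5 (points) | 6.0 | 3.0 | 1.5 | 0.75 |
| Bias, t = 0.25 (points) | 9.0 | 6.75 | 5.1 | 3.8 |

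**5. Worked example (assumed counts).** Take 40 lesions with 5 true failures, so true control is 35/40 = 87.5%. Two of the failures are untested, and 3 controlled lesions have untested enlargement from treatment effect.

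- Only verified failures counted: (40 − 3)/40 = 92.5%.
- Unverified enlargement also counted as failure: (40 − 3 − 5)/40 = 80.0%.
- Unverified lesions: 2 + 3 = 5.

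The exact (Clopper-Pearson) 95% interval for 35/40 is 73.2% to 95.8%, ignoring clustering within patient.

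**6. Extreme case.** If 8 of 40 lesions enlarge and none is tested, 11.3.2 as written gives 40/40 = 100%. Counting them as failures gives 32/40 = 80%.

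**The case against.** - **Residual tumor is not failure.** Partial response and stable disease also leave tumor behind and count as control, so 11.3.1 may only govern what is measured. That reading is possible, and it makes the two sections unreconciled rather than flatly contradictory. It does not classify the untested lesion.
- **The enlargement is not lost.** LE is its own response category, and treated lesions are measured at each follow-up imaging. This is correct, and it is why the remedy is cheap. However, 12.4 and section 13 plan no use of LE.
- **The size is assumed.** This stands. The plan leans towards testing suspected progression, and with three or four chances at 50% the bias is under one lesion. The direction is better established than the amount.
- **False-positive PETs push the other way.** Against the truth, the net direction is therefore not guaranteed. Against full testing it is: failure requires a positive test, so fewer tests can only mean fewer recorded failures.
- **Counting all unverified enlargement as failure may do worse.** In the example it misses by 7.5 points, against 5.0 for the rule as written. This stands too, so the two rates should be read as a range, with neither put forward as the correct estimate.
- **The endpoint is secondary and descriptive in a 20-patient pilot.** This is true, and it limits the consequence.

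**Conclusion.** The point holds. As written, 11.3.2 scores an enlarging, untested treated lesion as controlled, and nothing elsewhere in the document changes that. This follows from the definitions alone.

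The size depends on a verification rate that the documents do not give. Under the assumptions shown, the bias at a true 88% runs from 0.75 points (four testing chances at 50% each) to 9.0 points (75% of true failures never verified). Shifts of this order lie within sampling error at 40 lesions, but relative to full testing they run one way.

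The primary toxicity endpoint is untouched, and no local control target is tested. Whether the result would look better or worse than the cited series cannot be judged, because their failure definitions are not given. The change should be made, but it is not critical to the trial's main purpose.

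**What to change.** 1. In 11.3.2, label LE without PET or biopsy as unverified enlargement, using a tested/untested flag completed at each assessment.
2. In 12.4, report local control (a) with only verified failures counted and (b) with unverified enlargement also counted as failure. Present the two as a sensitivity range and give the number of unverified lesions. Apply the same pair to time to recurrence, with the event date for unverified enlargement stated in advance.
3. State how the PET criterion is applied when there is no baseline PET.
4. Say whether the residual-tumor default in 11.3.1 bears on criterion 2 or only on measurement.
5. Clarify whether Involved Lobe Failure needs PET or biopsy in addition to LE.

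The cost is one flag on the response form, a second version of the local control results, one count and some redrafting. No PET, biopsy or CT is added. Treated lesions are already measured under 11.3.1. New marginal or involved-lobe lesions would need their dimensions recorded from CTs already scheduled.

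The drawback is that rate (b) will include some treatment effect and can be too low. With g the share of controlled lesions showing untested enlargement, rate (b) = (1 − f)(1 − g). At a true 88%, an assumed g of 5% gives 0.88 × 0.95 = 83.6%, and 20% gives 0.88 × 0.80 = 70.4%. The two rates may therefore lie far apart, and the report should say why.

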3.2 Conditions for Patient Ineligibility

- 3.2.1 Patients who have uncontrolled extra-pulmonary disease
- 3.2.2 Pregnant women
- 3.2.3 Patients who have greater than 5 pulmonary lesions at the time of study enrollment
- 3.2.4 Patients who have disease progression outside the lungs within 3 months of enrollment on the study.
- 3.2.5 Disease pathology other than sarcoma subtypes
- 3.2.6 Patients with a history of metastatic disease from a primary other than sarcoma

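### Section 11.3.2 cannot score a biopsy-proven new tumor beside the target as Marginal Failure on the scan that first shows it, and its biopsy criterion names carcinoma in a sarcoma-only trial

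*Combined protocol and SAP*

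**What the plan says.** The response table in 11.3.2 holds three failure rows that matter here.

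- **Marginal Failure (MF):** a measurable tumor that appears after treatment "within 1.0 cm of the treated PTV (see Section 6.4) and meeting the following two criteria". Criterion 1 is "Enlarging tumor dimensions corresponding to a 20% increase in the longest diameter compared to initial appearance on imaging evaluation". Criterion 2 is PET uptake similar to the staging PET, "OR the measurable tumor should be biopsied confirming viable carcinoma".
- **Primary Tumor Failure (PTF):** also two joint criteria. Growth is judged by the Local Enlargement (LE) rule: "At least a 20% increase in the LD of target lesion, taking as reference the smallest LD recorded since the treatment started". The second criterion is the same choice of PET or biopsy. MF is counted as PTF in the outcome analysis but recorded separately. Primary Tumor Control is the absence of PTF.
- **Involved Lobe Failure (ILF):** "Refers to the appearance of lung cancer after protocol therapy within the anatomical boundaries of the lobe". The row lists LE, PET avidity and biopsy. Local Failure is PTF or ILF, and Local Control is its absence.

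Section 3.2.5 makes ineligible "Disease pathology other than sarcoma subtypes". Section 11.2.2 calls for a chest CT before each visit and leaves PET at progression to the physician; on tissue it says "Biopsy is recommended although will be at the discretion of treating physician". Section 12.3 applies 11.3.2 lesion by lesion to define local and regional recurrence. Section 12.4 reports crude recurrence rates and time to recurrence.

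**The concern.** Histology is the firmest evidence of recurrence the plan can obtain, yet for a new tumor beside the target it does not count until the tumor has also grown by 20% from its own first measurement. The scan that reveals the nodule only sets the reference. The same criterion names a histology that the enrolled patients' disease does not have.

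Local control is the first secondary objective in 2.1.2, and the Introduction presents the study as documenting local control of sarcoma lung metastases. A scoring rule that delays or omits proven failures, and leaves two rows in conflict over one nodule, makes that rate and the time to recurrence depend on how each assessor reads the table.

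**Working it through.** The documents give no figure to reproduce on this point. The check is a reading of the rows followed by schedule arithmetic.

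**1. Logic of MF.** MF = growth AND (PET OR biopsy). At first appearance the diameter equals its own reference, so growth is 0% and MF is false whatever the biopsy shows. At least one later scan is required.

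**2. Size of the delay.** Visits are 6-monthly (11.2.1), with a window of ±1 month (table in 11.1). The gap between consecutive scheduled scans is nominally 6 months, from 6 − 1 − 1 = 4 to 6 + 1 + 1 = 8. An interim scan would shorten it, because criterion 1 does not require a scheduled CT. A 20% rise in diameter is a volume factor of 1.2³ = 1.728, or log₂(1.728) = 0.789 doublings. If growth is exponential and equal in all directions (an assumption), it shows at the next 6-month scan only when the volume doubling time is at most 6 / 0.789 = 7.6 months. Slower tumors are dated two or more scans late.

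**3. The overlap with ILF.** For a same-lobe nodule within 1.0 cm of the PTV, the ILF sentence can be parsed in two ways:

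| Reading of ILF | Biopsy alone enough? | Nodule biopsied at first appearance |
|---|---|---|
| LE and (PET or biopsy) | No | Not MF, not ILF: Local Control |
| (LE and PET) or biopsy | Yes | Not MF, but ILF: Local Failure, yet Primary Tumor Control |

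**4. Histology.** Read literally, a biopsy showing sarcoma does not satisfy MF, PTF or ILF, and a new primary lung carcinoma does. Only the biopsy route is affected. That route can be the only one available, because PET at progression is discretionary and, per the notes in 11.1, PET/CT may be omitted when not insured, which can remove the staging scan used as comparator.

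**5. Effect on the rate.** The Schema expects 40 tumors, so one lesion is 1/40 = 2.5 percentage points.

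The following is illustration only. Assume 40 lesions, first detection equally likely at 6, 12, 18 and 24 months, growth always visible on the next scan, no scan after 24 months and no rescue through ILF. One quarter of marginal recurrences then go unscored. The share of failures that are marginal is not given, so take 25% to 100%. Apparent control = 1 − F(1 − share/4)/40, where F is the true number of failures.

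- True control 88% (the sarcoma series in the Introduction): F = 40 × 0.12 = 4.8. Apparent control is 1 − 4.5/40 = 88.75% to 1 − 3.6/40 = 91.0%.
- True control 77.9% (the literature review in the Introduction): F = 40 × 0.221 = 8.84. Apparent control is 1 − 8.29/40 = 79.3% to 1 − 6.63/40 = 83.4%.

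If a CT at the 4–6 week visit makes five scans, the unscored fraction is one fifth. The ranges become 88.6% to 90.4% and 79.0% to 82.3%.

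**The case against.** **Biopsy-proven recurrences are counted as controlled.** A reader might infer this as fact. The documents do not settle it. The stated objective is local control, whose complement includes ILF, and ILF can be read to accept biopsy alone. On that reading a same-lobe marginal nodule is already a Local Failure, and Primary Tumor Control is not a named endpoint in 2.1.2, 12 or 13. This stands. It turns part of the point into an unresolved conflict between rows.

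**PTF has the same defect.** The structure is similar, but the effect is small. Section 11.2.2 raises PET and biopsy once progression is suspected, so growth usually comes first, and after a complete response the smallest diameter is zero, so any regrowth meets LE. Requiring growth in an irradiated lesion is a defensible choice for specificity. This stands, and the PTF growth rule should be left alone.

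**A nodule first seen at 24 months can never qualify.** That assumes a settled schedule. Section 11.2.1 says 2 years, the table in 11.1 prints 12 years, and 12.2 and 12.3 ask for at least 3 years of follow-up without scheduling a CT for it. Section 11.2.2 also implies a CT at the 4–6 week visit, which the table does not mark. What stands is narrower: without a later scan, the nodule cannot be MF.

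**No assessor would reject a sarcoma-positive biopsy over one noun.** Probably so. The wording looks written for primary lung cancer, the PTF row elsewhere speaks of cancer generally, and the PET route does not use the word. But if assessors read it as viable tumor, the MF growth condition and the late date remain.

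**It is a descriptive secondary endpoint in a 20-patient pilot.** True. The toxicity endpoint is untouched, and disease-free survival in 12.3 carries no stated growth condition.

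**Conclusion.** The point holds for MF and for the histology wording. As written, a biopsy-proven new tumor within 1.0 cm of the PTV cannot be MF when first seen. It is dated about 6 months late (4–8 with the windows, if there is no interim imaging and growth is fast enough), or is not scored MF if it is treated first or not rescanned. Whether it still enters Local Failure depends on an ambiguous ILF sentence and on being in the same lobe.

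The direction is mainly toward higher or later-failing local control. The one opposite effect is that a new primary lung carcinoma would count as failure. The documents do not say how many lesions are affected. The firm figure is 2.5 percentage points per lesion if 40 tumors are treated; the ranges above rest on assumed shares and should not be quoted as an estimate of bias. The correction should be made because the rule misdates or misclassifies as written and costs little to repair.

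**What to change.** Amend the table in 11.3.2 and the matching response form:

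1. In the PTF, MF and ILF rows, replace viable carcinoma with viable sarcoma and, in ILF, lung cancer with sarcoma metastasis. State that a new primary lung cancer is not local failure.
2. For a new tumor within 1.0 cm of the PTV, let a biopsy showing viable sarcoma count as MF without the 20% growth criterion, dated to the first post-treatment imaging that showed it.
3. Keep growth plus PET avidity as an MF route whether or not a biopsy was done, so that a growing, avid tumor with a negative or nondiagnostic biopsy is not lost. Date it to first appearance once confirmed.
4. State that MF takes precedence over ILF within 1.0 cm of the PTV, and write out the and/or structure of the ILF sentence.

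Apart from the histology word, leave PTF in the treated lesion unchanged. Letting biopsy suffice there could fail shrinking lesions with residual viable cells, and dating to first imaging would point to the pretreatment scan.

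This needs no extra scan or biopsy. The cost is a wording change, rescoring of any lesion already assessed, and possibly a slightly less favourable local control rate. One gap remains: a nodule first seen on the last scan and not biopsied still cannot be scored MF.
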